APPENDIX IV: VISIT SCHEDULE FOR RASH MANAGEMENT IN PEDIATRIC SUBJECTS

This visit schedule summarizes the visits and assessments to be performed in case of rash. NOTE: At the investigator's discretion, whenever follow-up visits, laboratory tests or digital photos are NOT required by this schedule, these evaluations may be performed at the investigators discretion, if clinically indicated. All results should be documented in the study CRFs.

	Grade 1 Rash	Grade 2 Rash	Grade 3/4 Rash
Day 0 ¹	
 Study medication MAY be CONTINUED Unscheduled visit for initial rash evaluation REQUIRED. Referral to dermatologist ONLY IF rash diagnosis uncertain (within 24-48hr). 	
 Study medication MAY be CONTINUED. Unscheduled visit for initial rash evaluation REQUIRED. Referral to dermatologist REQUIRED (within 24-48hr). Blood sample for safety evaluations by local laboratory ONLY IF requested by investigator or dermatologist. Biopsy ONLY IF required by dermatologist. 	
 Study medication MUST be permanently DISCONTINUED. Re-challenge is NOT ALLOWED. Unscheduled visit for initial rash evaluation REQUIRED. Referral to dermatologist REQUIRED (within 24-48hr). Blood sample for safety evaluations by local laboratory. Biopsy REQUIRED within 24 hours after onset of rash Digital pictures REQUIRED.
Day 1	
 Follow-up visit REQUIRED 	
 Follow-up visit REQUIRED 	
 Follow-up visit REQUIRED. Digital pictures REQUIRED.
Day 2	No follow-up visit required	
 Follow-up visit REQUIRED 	
 Follow-up visit REQUIRED.
Day 3	No follow-up visit required	No follow-up visit required	
 Follow-up visit REQUIRED.
Day 4	No follow-up visit required	No follow-up visit required	
 Follow-up visit REQUIRED.
Day 5	No Rash follow-up visit required ²	No Rash follow-up visit required ²	
 Follow-up visit REQUIRED.
Day 6	No Rash follow-up visit required	No Rash follow-up visit required	No Rash follow-up visit required
Day 7	
 Follow-up visit REQUIRED. 	
 Follow-up visit REQUIRED. 	No Rash follow-up visit required
Further Visits	If rash is unresolved after second follow-up visit, subject should be referred to a dermatologist for further evaluation.	If rash is unresolved after second follow-up visit, subject should be referred to a dermatologist for further evaluation.	Weekly follow-up visits REQUIRED (with digital pictures) until resolution of Grade 3-4 rash to Grade \leq 2 rash (further follow-up visits according to Grade 1 or Grade 2 rash instructions).
Upon Rash Resolution/ Stabilization ³	Complete final rash assessment pages in the CRFs	Complete final rash assessment in the CRFs	Complete final rash assessment pages in the CRFs

Footnotes:

1 Note that Day 0 of the rash is the first day of investigator assessment and not the first day of rash as reported by the subject.

2 In case rash progresses from a Grade 1 or a Grade 2 to a higher Grade, start follow-up schedule for Grade 2, 3 or 4 rash as appropriate.

APPENDIX V: GRADING FOR PR AND QTc INTERVALS

A. TABLE TO DETERMINE 98TH PERCENTILE FOR PR RESULTS IN LEAD II

This table should be used when evaluating ECGs for subjects <8 years of age. This table is to be followed in conjunction with exclusion criterion 4.211, toxicity management section 6.15, and Appendix IA-ID. If you have any questions regarding the implementation of this table, please contact the core protocol team at [contact].

Subject's Age	Normal PR-Interval (milliseconds)
≥3 to <6 months	≤ 150
≥6 to <12 months	≤ 160
≥1 to <3 years	≤ 150
≥3 to <5 years	≤ 160
≥5 to <8 years	≤ 160

Source: The Electrocardiogram in Infants and Children: A Systematic Approach. Arthur Garson, Jr. Lea and Febiger Publishers. Philadelphia, 1983. (Original table, labeled A-3 in the book, was modified by the IMPAACT P1090 Protocol Team to suit the specific needs of the protocol)

B. DETERMINING ADVERSE EVENT GRADING OF PROLONGED QTc INTERVALS

Please refer to the DAIDS toxicity tables for adverse event grading of prolonged QTc intervals. The DAIDS Table for Grading the Severity of Adult and Pediatric Adverse Events, (DAIDS AE Grading Table), Version 1.0, December 2004, Clarification August 2009, must be used and is available on the RSC website at (<http://rsc.tech-res.com/safetyandpharmacovigilance/>).

C. DETERMINING ADVERSE EVENT GRADING OF PROLONGED PR RESULTS

Please refer to the DAIDS toxicity tables for adverse event grading of prolonged PR intervals. The DAIDS Table for Grading the Severity of Adult and Pediatric Adverse Events, (DAIDS AE Grading Table), Version 1.0, December 2004, Clarification August 2009, must be used and is available on the RSC website at (<http://rsc.tech-res.com/safetyandpharmacovigilance/>).

APPENDIX VI: SUPPLEMENTAL TOXICITY TABLE FOR GRADING SEVERITY OF NEUROLOGIC ADVERSE EVENTS

For the purposes of P1090, the following parameter and grading criteria are to be used in conjunction with the DAIDS Table for Grading the Severity of Adult and Pediatric Adverse Events, dated December 2004, Clarification August 2009, in grading neurologic adverse events. This parameter supersedes Row 1 (alteration in personality-behavior or in mood) and Row 2 (altered mental status) of the neurologic section of the DAIDS Toxicity Table.

	Grade 1	Grade 2	Grade 3	Grade 4
Sleepiness, lethargy, irritability	Transiently lethargic, irritable or fussy (above usual norm), but otherwise normal routine.	More sleeping or crying than usual, not on normal routine without alternate explanation.	≥7 days of a change in personality without alternate explanation and confirmed by objective observation by study staff OR Somnolent, needs to be stimulated to take feedings.	Somnolent, unable to be stimulated to take feedings. OR Inconsolable irritability or crying with unusually high pitch or screaming for > 3 hours

APPENDIX VII-A: SUPPLEMENTAL TOXICITY TABLE FOR GRADING SEVERITY AND MANAGEMENT OF ADULT AND PEDIATRIC CUTANEOUS ADVERSE EXPERIENCES

Since cutaneous adverse events are of particular interest for this drug, the following guidelines on monitoring and management should be followed. Please refer to Appendix IV which describes the visit schedule for management of cutaneous adverse events.

NOTE: These management guidelines are NOT applicable to rashes with clear alternative etiology, such as chicken pox, impetigo and cutaneous HSV. Cetirizine, levocetirizine, topical corticosteroids and anti-pruritic agents will be allowed at the investigator's discretion for all grades of rashes.

CUTANEOUS ADVERSE EVENTS			
	Grade	Description	Subject Management
Cutaneous rash / reaction	GRADE 1	Localized macular rash	
 Subjects with Grade 1 or Grade 2 rash may continue etravirine or temporarily interrupt therapy at the investigator's discretion. Close clinical follow up is recommended to monitor progression of rash.
	GRADE 2	Diffuse macular, maculopapular or morbilliform rash or target lesions	
 Subjects with Grade 1 or Grade 2 rash may continue etravirine or temporarily interrupt therapy at the investigator's discretion. Close clinical follow up is recommended to monitor progression of rash. All subjects with Grade 2 rash must be seen by a dermatologist within 24 to 48 hours.
	GRADE 3	
 Diffuse macular, maculopapular or morbilliform rash with vesicles or limited number of bullae Cutaneous reaction /rash with superficial ulceration of mucous membrane limited to 1 mucosal site Cutaneous reaction/rash with at least 1 of the following: 
 Elevations of ALT/AST >2x baseline but at least 5x upper limit of laboratory normal range (ULN) Fever $\geq 38^{\circ}\text{C}$ or 100.4°F Serum sickness-like reaction Eosinophil count $>1000/\text{mm}^3$ 	
 Subjects experiencing a Grade 3 rash or cutaneous event must have etravirine discontinued permanently; but should remain on study for safety follow-up OBR should be held at the discretion of the site investigator Subjects must also be evaluated by a dermatologist within 24 to 48 hours The protocol team should be notified of a Grade 3 event at [contact]

	GRADE 4	
 Extensive or generalized bullous lesions Stevens-Johnson syndrome (SJS) Ulceration of mucous membrane involving 2 or more distinct mucosal sites Toxic epidermal necrolysis (TEN) 	
 Subjects experiencing a Grade 4 rash or cutaneous event must have etravirine discontinued permanently; but should remain on study for safety follow-up OBR should be held at the discretion of the site investigator Subjects must also be evaluated by a dermatologist within 24 to 48 hours The protocol team should be notified of a Grade 4 event at [contact]
--	---------	--	--

APPENDIX VII-B: SUPPLEMENTAL TOXICITY TABLE FOR GRADING SEVERITY AND MANAGEMENT OF ADULT AND PEDIATRIC ACUTE SYSTEMIC ALLERGIC ADVERSE EXPERIENCES

ACUTE SYSTEMIC ALLERGIC ADVERSE EXPERIENCES			
	Grade	Description	Subject Management
Urticaria	GRADE 1	Localized urticaria with no medical intervention indicated	Subject may continue intake of etravirine
	GRADE 2	
 • Localized urticaria with medical intervention indicated • Mild angiodema with no medical intervention indicated 	Subject may continue intake of etravirine
	GRADE 3	
 • Generalized urticaria or angioedema with medical intervention indicated • Symptomatic mild bronchospasm 	
 • Subjects with Grade 3 acute systemic allergic reactions will be permanently discontinued from the investigational medication (ETR) and background regimen but will be followed on study on a modified schedule (Appendix IE) for safety outcomes • Subjects will be treated as clinically appropriate per the local physician
	GRADE 4	
 • Acute anaphylaxis • Life-threatening bronchospasm • Laryngeal edema 	
 • Subjects with grade 4 acute systemic allergic reactions will be permanently discontinued from the investigational medication (ETR) AND background regimen (OBR) but will be followed on study on a modified schedule (Appendix IE) for safety outcomes • Subjects will be treated as clinically appropriate per the local physician • The protocol team should be notified of a Grade 4 event at [contact]

1 INTRODUCTION

This Primary Statistical Analysis Plan (SAP) describes the primary and secondary outcome measures of P1090 that will be included in the primary manuscript, and which address the primary and secondary objectives of the study. The Primary SAP outlines the general statistical approaches that will be used in the analysis. It has been developed to facilitate discussion of the statistical analysis components among the study team, and to provide agreement between the study team and statisticians regarding the statistical analyses to be performed and presented in the Primary Statistical Analysis Report. It also describes the results for the primary and secondary outcome measures that will be posted on ClinicalTrials.gov. It is recognized that this statistical analysis plan (SAP) may be modified by the Study Team as new information becomes available.

The P1090 SAPs, Version 1 (dated 11/30/2011), Version 2 (dated 12/7/2018), and the current version, do not address the interim data analyses for Janssen's submissions to regulatory agencies. As mentioned in P1090 protocol section 8.6324, Janssen performs these interim data analyses for their regulatory submissions, using P1090 study datasets provided to Janssen by the IMPAACT Data Management Center.

Data for the Primary Statistical Analysis Report will be downloaded once the last participant of the last cohort has completed the Week 48 study visit, all queries have been resolved, and the database frozen for analysis. The Primary Statistical Analysis Reports will be used for submission of results to ClinicalTrials.gov. Results for primary outcomes are required to be submitted within one year of the primary completion date (PCD), which is the date the last participant is examined for the purposes of data collection for the primary outcome measure. For this study, the PCD is based on 48 weeks of treatment. A second submission to ClinicalTrials.gov will be done within one year after the last enrolled participant reaches Week 288 the last visit of the long-term safety follow-up) at which time point the adverse event tables will be updated.

2 STUDY DESIGN

This is a Phase I/II, multicenter, open label 48 week pharmacokinetic, safety, tolerability and antiviral study of etravirine in combination with at least 2 active ARVs, including a boosted PI and NRTIs for treatment experienced HIV-1-infected infants and children ≥ 2 months to < 6 years cohorts.

The study will, in a sequential manner, accrue subjects for an initial dose finding intensive PK component for age related cohorts. It is expected that approximately 50 subjects will be accrued, to yield a minimum of 36 evaluable subjects (a minimum of 12 subjects in each cohort). Up to 18 subjects may be enrolled into Cohort I. The total sample size will depend upon the number needed to complete the dose finding stage of the study and the number of subjects required for regulatory approval of etravirine in these populations.

Evaluable will be defined as having been treated exclusively on the dose determined to be optimal for a given age cohort and having either completed 24 (or 48) weeks of exposure to the study drug or having been classified as a safety failure, due to a study drug related adverse event occurring during the first 24 (or 48) weeks of treatment.

The P1090 core protocol team will be responsible for reviewing the PK and safety data and approving the dose selection for each full and mini-cohort. The P1090 core protocol team will consist of the protocol chair and co-chairs, clinical trials specialist, NIAID and NICHD Medical Officers, data manager, pharmacologists, pharmacist, statisticians and Janssen representatives.

This study is designed to determine the appropriate etravirine dose for HIV-1-infected infants and children and to evaluate the PK, safety and tolerability of etravirine in this population. Etravirine (ETR) will be administered as 25 mg scored tablets and/or 100 mg tablets swallowed as a whole or dispersed in an appropriate liquid vehicle (see Section 5.2). ETR will be started concurrently with an optimized background regimen (OBR), while OBR will be based on clinical status, treatment history, resistance data and availability of appropriate pediatric dosing and formulations.

Children will be stratified by age, as follows:

- Cohort I: ≥ 2 year to < 6 years who are treatment experienced*
- Cohort II: ≥ 1 year to < 2 years who are treatment experienced*
- Cohort III: ≥ 2 months to < 1 year who are treatment experienced*, †

[figure not shown]
*Treatment experienced children on a failing combination antiretroviral regimen (containing at least 3 ARVs) for at least 8 weeks OR Treatment experienced children on a treatment interruption of at least 4 weeks with a history of virologic failure while on a combination antiretroviral regimen (containing at least 3 ARVs)

† Subjects below 6 months of age will only be enrolled upon availability of initial safety and PK data from subjects between 6 months and 1 year of age.

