Additional Safety Data

Safety data derived from pooling of the results of 1,043 adult HIV-1-infected treatment-experienced subjects enrolled in the Phase III trial indicated that ETR is generally safe and well tolerated. The most common AEs reported during ETR treatment with the selected dose were rash (any type, 16.9%; Grade 2 to 4 rash 9%), diarrhea (any Grade 1: 9.4%; Grade 2 to 4: 5.2%), nausea (any Grade, 13.9%), and headache (Grade 1: 2.2%; Grade 2 to 4: 2.7%).

With the exception of rash, the incidence of AEs and laboratory abnormalities were generally comparable to placebo. Table 5 describes these results.

A recent double-blind placebo-controlled trial of ETR 400 mg QD versus EFV in HIV-infected adults, naïve to ART, compared neuropsychiatric side effects in the two arms. At week 12, 16.5% of ETR treated subjects reported at least one grade 1 to 4 treatment related neuropsychiatric AE, compared to 46.2% in the EFV treated subjects; for grade 2 to 4 AEs, the incidence was 5.1% in the ETR arm and 16.7% in the EFV arm (32).

Twenty-six subjects (2.1%) died during the study while on ETR; 25 of which were judged not, or unlikely, related to ETR therapy. One death, due to myocardial infarction with cardio respiratory failure, in a subject with risk factors for premature coronary artery disease, was considered possibly related to ETR therapy (18).

The rashes tended to be mild to moderate; they usually occurred in the second week of therapy, and resolved within 1 to 2 weeks on continued therapy. In the adult phase III trials, the cumulative incidence of Grade 3 and 4 rashes was 1.3% for subjects on ETR and 0.2% for those on placebo. A total of 2% of subjects discontinued study due to rash. There were no cases of Stevens Johnson Syndrome (SJS) or toxic epidermal necrolysis (TEN) reported due to ETR in any of the Phase IIb/III studies (18).

In August of 2009, the FDA issued a warning to physicians, related to the occurrence of severe, potentially life threatening, and fatal skin rashes (erythema multiforme, SJS and TEN) linked to ETR use during the post marketing period. Prescribing information has been updated to reflect this information. The rate of SJS and TEN was < 0.01% each. The hypersensitivity reactions manifested as rash along with constitutional findings. At times, evidence of impending organ failure existed. The current recommendation is to stop ETR at the onset of severe skin rash, with careful clinical monitoring (13).

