8.0 STATISTICAL CONSIDERATIONS

8.1 General Design Issues

This is a Phase I/II multicenter, open label study with primary objectives of assessing the safety/tolerability and pharmacokinetics of ETR in combination with optimized background regimen (OBR) administered to HIV-infected treatment-experienced children within the age range of ≥ 2 months to < 6 years.

Hypothesis: ETR will be safe, well tolerated, will have pharmacokinetics comparable to adults and will demonstrate antiviral activity when used with an optimized background therapy in HIV-1-infected, treatment experienced infants and children.

The sample will be stratified into the following age groups:

Cohort I	≥ 2 years to < 6 years of age who are treatment experienced*
Cohort II	≥ 1 year to < 2 years of age who are treatment experienced*
Cohort III:	≥ 2 months to < 1 year who are treatment experienced* †

*Treatment experienced children on a failing combination antiretroviral regimen (containing at least 3 ARVs) for at least 8 weeks OR Treatment experienced children on a treatment interruption of at least 4 weeks with a history of virologic failure while on a combination antiretroviral regimen (containing at least 3 ARVs)

†Subjects below 6 months of age will only be enrolled upon availability of initial safety and PK data from subjects between 6 months and 1 year of age.

A minimum of 12 subjects will be enrolled into each cohort of the study. Up to 18 subjects may be enrolled into Cohort 1. The total sample will include at least 36 evaluable subjects who have been treated exclusively at the doses judged to be optimal for their age cohorts.

NOTE: For the Week 24 (or Week 48) analysis, evaluable will be defined as having been treated exclusively on the dose determined to be optimal for a given age cohort and having either completed 24 (or 48) weeks of exposure to the study drug or having been classified as a safety failure, due to a study drug related adverse event occurring during the first 24 (or 48) weeks of treatment.

Accrual to the study will follow an algorithm in which younger children's (Cohort II and Cohort III) exposure to the study medication is contingent upon the older age cohort (Cohort I) having passed the safety criteria. In addition, sufficient pharmacokinetic data will be required to determine the starting dose for the younger cohort (see Section 3.3-3.4 for details).

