8.6 Analyses

8.61 Summary of Dose Finding Data

The analysis of dose finding data will consist of descriptive statistics summarizing the safety and PK data from the dose finding phase of the study. (See Section 9.0 for PK analysis). The safety data will be analyzed by cohort and will present the results of the safety evaluations applied to each starting dose regimen tested within each cohort, including information indicating which starting doses have passed or failed the safety guidelines. For each starting dose within each cohort, every adverse event of Grade 3 or higher will be listed, along with subject demographics, the dose prescribed to the patient at the time of the event and the protocol team's assessment of the probability that this event was due to the study treatment (not related, probably not related, possibly related, probably related or definitely related).

8.62 Analysis of Data Representing Exposure to the Doses Judged to be Optimal for Each Cohort

These analyses will be stratified by cohort. The findings will be presented in both in aggregate and broken down by cohort, with estimates bounded by 95% confidence limits. Given that the small sample sizes within cohorts will provide limited power for statistical tests of differences across age cohorts, interpretation of the results will depend upon whether differences across cohorts are great enough to be considered to be clinically significant. If no such differences are observed, then the clearest interpretation of the findings will come from the aggregated data, where analyses will have the greatest statistical precision. However, if results vary across cohorts to a clinically important extent, interpretation of results should take into account the issues represented by the stratification factor.

8.63 Primary Analyses - performed on data through the Week 24 and Week 48 visit

8.631 Safety

The primary safety analysis will include only subjects whose total exposure to ETR has been at the dose judged to be optimal for their cohorts. Subjects whose doses have been adjusted for inadequate PK will be excluded. Subjects who have been removed from treatment or have had their doses reduced due to toxicities while on the optimal dose will be included and treated as safety failures in the primary safety

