analysis. Additional analyses will look at the combined data from subjects whose doses failed and those who have been treated solely at the optimal doses determined for their cohorts and without individual PK determined dose adjustments. Sensitivity analyses will be performed to determine whether the exclusion of subjects whose doses have been adjusted creates a selection bias which impacts upon any results.

Each subject's safety data will be summarized as: the worst grade of adverse event experienced during the first 24 weeks (and 48 weeks) of exposure to the optimal dose of the study treatment and the worst grade of adverse event judged to be at least possibly related to study treatment during this time period. Frequency distributions of these safety outcomes will be presented in the aggregate and broken down by age. Listings of all Grade 3+ events will be provided, broken down by type of toxicity (hepatic, hematologic etc.).

The proportions of subjects experiencing Grade 3+ adverse events will be presented in aggregate and broken down by age cohort, with these proportions bounded by exact 95% confidence intervals. Similar analyses will present the proportions of subjects exhibiting Grade 3+ events which have been judged to be at least possibly related to study medication, again bounded by exact 95% confidence intervals.

8.632 Key Secondary Analyses

8.6321 Viral Load

Virologic outcomes, based on HIV-1 RNA (copies/ml), will be assessed at weeks 8, 12, 24 and 48. The criteria for success are: at least a 0.5 log₁₀ reduction in HIV-1 RNA (copies/ml) at week 8, at least a 1 log₁₀ reduction in HIV-1 RNA (copies/ml) at week 12 and either HIV-1 RNA ≤ 400 copies/ml or at least a 2 log reduction in HIV-1 RNA at weeks 24 and 48.

For regulatory submissions, at each of these time points the primary definition of virologic outcome will be calculated according to a Missing, Switch or Discontinuation = Failure (MSDF) algorithm – as codified by the FDA's snapshot algorithm. Subjects may be classified as virologic failures if they have missing HIV-1 RNA data throughout the window surrounding the time point of interest. (This window and related details will be defined in the analysis plan.) In addition subjects will be classified as virologic failures at any of these time points if they meet any of the following conditions prior to that time point:

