5 ENDPOINTS AND OUTCOME MEASURES

Primary Endpoints:

Toxicity Endpoints:

- Termination from treatment due to a suspected adverse drug reaction (SADR)
- Adverse events of Grade 3 or higher severity
- Death

Pharmacokinetic Endpoint:

- Failure to meet PK targets (specified in Section 9.0)

Secondary Endpoints:

- Adverse events of Grade 3 or higher severity judged to be at least possibly attributable to the study medications
- Confirmed failure to suppress plasma HIV-1 RNA to ≤ 400 copies
- AND
- Failure to achieve at least a 2 log reduction (from baseline) in HIV-1 RNA at weeks 24 and/or 48 (confirmed in 1 to 4 weeks)
- Treatment discontinued due to toxicity or virologic failure
- Change in optimized background regimen due to virologic failure
- New onset OI or AIDS diagnosis
- Decline in absolute CD4 percent of $> 5\%$ any time after 12 weeks of therapy

Primary Response Variables:

- Pharmacokinetic parameters - AUC12h

Secondary Response Variables:

- Plasma HIV-1 RNA (copies/mL)
- CD4 counts and percent
- CD4/CD8 ratio and percent
- Genotypic and phenotypic measures of resistance at virologic failure and at early discontinuation
- Pharmacokinetic parameters - C12h and Cmax

Exploratory Response Variables:

- Patient-specific CYP gene profiles.

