6.2 Safety

- Summary of Dose Finding Data (Through Week 4 – the point up to which the safety criteria are applied)

Descriptive statistics summarizing the safety data during the dose finding phase of the study. The safety data will be broken down by cohort and will present the results of the safety evaluations applied to each starting dose tested within each cohort, including information indicating which starting doses have passed or failed the safety guidelines. For each starting dose within each cohort, every adverse event of grade 3 or higher will be listed, along with patient demographics, the dose prescribed to the patient at the time of the event and the protocol team's assessment of the probability that this event was due to the study treatment.

- Analysis of Data Representing Exposure to the Doses Judged to be Optimal for Each Cohort

Primary Analysis of Safety: consists of data from “evaluable” patients only, performed on data through the weeks 24 and 48 visit at the final dose.

Each patient's safety data will be summarized as: the worst grade of adverse event experienced while on the first 24 and 48 weeks on the optimal dose of the study treatment and the worst grade of adverse event judged to be at least possibly due to study treatment during this time

period. Frequency distributions of these safety outcomes will be presented in the aggregate and broken down by cohort. Listings of all Grade 3+ events will be provided, broken down by type of toxicity (hepatic, hematologic, etc.).

The proportions of subjects experiencing grade 3+ adverse events will be presented in aggregate and broken down by Cohort, with these proportions bounded by exact 95% confidence intervals. Similar analyses will present the proportions of subjects exhibiting grade 3+ events which have been judged to be at least possibly related to study medication, again bounded by exact 95% confidence intervals.

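### An early leaver on the final dose with an unrelated Grade 3+ event is missing from the SAP's primary Week 24/48 Grade 3+ proportion, although that endpoint is all-cause and Protocol 8.631 describes a wider set

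*SAP*

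**What the plan says.** **The analysis set.** SAP 6.2 begins "Primary Analysis of Safety: consists of data from" evaluable patients and restricts it to them, through Weeks 24 and 48 at the final dose. SAP 2 defines evaluable as treated exclusively at the optimal dose and having either "completed 24 (or 48) weeks of exposure to the study drug or having been classified as a safety failure". Protocol 8.1 has the same definition and ties the second route to cause: "having been classified as a safety failure, due to a study drug related adverse event".

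**The endpoints.** SAP 5 and Protocol 8.21 list "Adverse events of Grade 3 or higher severity" and death as primary toxicity endpoints without attribution. Attributable Grade 3+ events are a separate, secondary endpoint. The third primary toxicity endpoint, termination for a suspected adverse drug reaction, is drug-related by definition.

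**The other description of the set.** Protocol 8.631 says the primary safety analysis "will include only subjects whose total exposure to ETR has been at the dose judged to be optimal" for the cohort. It excludes children adjusted for inadequate PK and adds: "Subjects who have been removed from treatment or have had their doses reduced due to toxicities while on the optimal dose will be included", as safety failures. It states neither a completion condition nor a relatedness condition.

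**What else is reported.** SAP 6.1 gives the frequency, list and causes of deaths, not limited to evaluable children. Protocol 8.1 plans secondary analyses of all safety data to 24 and 48 weeks and to study end. SAP 6.2 plans a similar analysis of all subjects through 5 years. Protocol 8.631 also plans this: "Sensitivity analyses will be performed to determine whether the exclusion of subjects whose doses have been adjusted creates a selection bias".

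**The concern.** The primary endpoints are all-cause, but the set on which they are estimated filters non-completers by cause. In an open-label, single-arm trial, membership then depends partly on outcome and on a relatedness judgement. The exact interval describes children who completed the period or failed for a drug-related reason, not the children started on the final dose.

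The SAP governs the primary report and the registry posting, which use data taken once the last child has completed Week 48 (SAP 1). At that point it offers no all-treated proportion to set beside the evaluable one. The 8.631 sensitivity analysis does not fill the gap, because it concerns dose-adjusted children only. Because 8.1 and 8.631 describe the set differently, two analysts could also build different primary sets from the same data.

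**Working it through.** **Step 1. Who is in the set.** The two descriptions, applied to a child started on the final dose with no PK-guided adjustment:

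| Child | Evaluable (SAP 2, Protocol 8.1) | Protocol 8.631 read alone |
|---|---|---|
| Unrelated Grade 3+ event, stays on drug to the cut-off | In | In |
| Stops early for a drug-related event | In | In, as safety failure |
| Removed early for an unrelated toxicity | Out | In, as safety failure |
| Unrelated Grade 3+ event, then leaves early for another reason, or dies of an unrelated cause | Out | In (dose criterion only) |
| Dose reduced for toxicity | Out (not exclusively at the optimal dose) | In, as safety failure |

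A child who leaves between Weeks 24 and 48 stays in the Week 24 set and drops out of the Week 48 set only.

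**Step 2. Reproduce the plan's figure.** Protocol Table 7 gives 4/36 (11%) with limits 3% to 26%. The Clopper-Pearson lower limit is the 0.025 quantile of Beta(x, n-x+1); the upper is the 0.975 quantile of Beta(x+1, n-x). With x = 4 and n = 36 this gives 3.1% to 26.1%. All 12 rows of Table 7 reproduce to rounding.

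**Step 3. Put leavers back.** The documents do not give the number of early leavers on the final dose. Protocol 8.42 expects about 50 enrolled for 36 evaluable, so 50 - 36 = 14 may fall outside the set, but that covers failed doses and every other reason. I assume L leavers, e of them with an unrelated Grade 3+ event; the proportion is (4+e)/(36+L).

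| L | e | Proportion | Exact 95% CI |
|---|---|---|---|
| 0 | 0 | 4/36 = 11.1% | 3.1%-26.1% |
| 1 | 1 | 5/37 = 13.5% | 4.5%-28.8% |
| 4 | 0 | 4/40 = 10.0% | 2.8%-23.7% |
| 4 | 1 | 5/40 = 12.5% | 4.2%-26.8% |
| 4 | 4 | 8/40 = 20.0% | 9.1%-35.6% |

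Within one cohort, adding one such child turns 1/12 = 8.3% (0.2%-38.5%) into 2/13 = 15.4% (1.9%-45.4%).

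**Step 4. Direction.** The proportion rises only if e/L exceeds 4/36. With L = 4 the break-even is 4 x 4/36 = 0.44 events: no event lowers the figure and one or more raises it.

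**Step 5. Follow-up time.** The crude 4/40 treats briefly followed leavers as event-free. Assume 48 weeks of follow-up for evaluable children and 16 for leavers (leaving at Week 12, plus the 4 weeks after stopping in Protocol 3.7), with 52.18 weeks per year. The evaluable set has 36 x 48/52.18 = 33.1 child-years, so 4 events give 12.1 per 100. The leavers add 4 x 16/52.18 = 1.2, making 34.3 child-years; 4, 5 or 8 events then give 11.6, 14.6 or 23.3 per 100. The pattern matches Step 3.

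**The case against.** The strongest reply is that the set is a declared choice. Protocol 8.1 says the primary safety analyses focus on exposure to the optimal dose for 24 and 48 weeks, with all-data analyses secondary. Protocol 3.3 replaces children who stop for reasons other than ETR toxicity. The SAP says it outlines general approaches, so its silence need not cancel the protocol's commitments. Under Protocol 6.1, definitely unrelated events may not lead to interruption of drug, which narrows the route out of the set. All of this stands, and it is why the evaluable analysis need not be demoted; which set is called primary is partly a matter of preference. It does not supply a Week 24/48 all-treated proportion in the SAP, nor settle the conflict between 8.1 and 8.631.

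A reader might infer that an unrelated early death is invisible, or that the primary death figure must be zero. The documents do not support that. No death proportion is specified for the evaluable set, and SAP 6.1 reports deaths for all children. Any death also suspends accrual for committee review (Protocol 8.521). Protocol 8.631 read alone would keep the child in, and a child already classed as a drug-related safety failure who later dies of another cause also stays in.

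A reader might also take the adult death rate in Protocol Table 5 as a forecast for this trial. It comes from another population, and the trial in 6 to 17 year olds had no deaths (Protocol 1.32). It is not used here.

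**Conclusion.** The point holds for one planned output, the Grade 3+ proportion in the primary safety set, and for the conflict between two descriptions of that set. An early leaver on the final dose with an unrelated Grade 3+ event, including a fatal one, is left out of it at that time point under the SAP's definition. The events themselves remain visible elsewhere.

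A systematic understatement of toxicity is not shown. Under four assumed leavers the shift is from 11.1% to 10.0% or 12.5% with no event or one, well inside the 3.1%-26.1% interval. It reaches 20.0% only if all four had events, which nothing in the documents suggests. The leaver count, their events and their follow-up are assumptions. This should be fixed because the endpoint and the analysis set disagree and the remedy is cheap, not because a large error is expected.

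**What to change.** 1. In SAP 6.2, add Week 24 and Week 48 all-cause Grade 3+ and death proportions with exact 95% CIs for all children started on the final dose, whatever the attribution or completion. Place them beside the evaluable-set result and show follow-up time. State that children with PK-guided dose adjustment are handled as planned in Protocol 8.631, and show the result with and without them, since excluding them is also a selection made after treatment starts.
2. Carry the all-data secondary analysis of Protocol 8.1 and the sensitivity analysis of Protocol 8.631 into the SAP.
3. Reconcile Protocol 8.631 with the definition of evaluable in Protocol 8.1 and SAP 2 on three questions: whether completion is required, whether a safety failure must be drug-related, and whether a child dose-reduced for toxicity belongs to the set.

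The cost is wording in both documents and one extra table from data already collected. The added figure may look slightly less favourable. Because leavers are followed for only about 4 weeks after stopping ETR, apart from continued follow-up of unresolved events, it should not be read without the follow-up time.
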